### 8.2.3 Exploratory Endpoints

Consistent with the first three, exploratory objectives described in Section 2.3, the following exploratory endpoints will be assessed.

- Perceived drug-hormone interactions: Questions on beliefs about drug interactions between antiretroviral agents and gender-affirming hormonal therapy collected at enrollment and quarterly follow up visits.
- Experience in intervention trial: Self-reported experiences of participating in an interventional study that includes biomedical and behavioral assessments, including the social impact of participation. Qualitative and quantitative evaluations will be performed at the termination visit.

Consistent with the exploratory study objective to assess safety of the intervention, the following endpoint(s) will be assessed:

- Reasons for discontinuation of any of the study products (GAHT, Truvada®, Descovy®).

[figure not shown]
- Grade 3 and above adverse events.
- Social harms reported by participants in the intervention arm.
- Additional exploratory endpoints will use laboratory assessments to characterize incident HIV infections. These assessments may include viral load testing, HIV drug resistance testing, ARV drug testing, phylogenetic analysis, and analysis of the host response to HIV infection.

Please refer to Section 8.7.2 for information on the exploratory endpoint related to the potential impact of hormonal therapy on PrEP concentrations.

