#### **7.6 Social Impact Reporting**

It is possible that participants' involvement in the study could become known to others, and that a social impact may result (i.e., because participants could be perceived as being HIV-infected or at risk or "high risk" for HIV infection). For example, participants could be treated unfairly, or could have problems being accepted by their families and/or communities. A social impact that is reported by the participant and judged by the IoR/designee to be serious or unexpected will be reported to the responsible site's IRBs at least annually, or according to their individual requirements. Social impacts will be collected and reported on applicable eCRF(s) during regular visits. In the event that a participant reports a social impact, every effort will be made by study staff to provide appropriate care and counseling to the participant as necessary, and/or referral to appropriate resources for the safety of the participant. Each site will provide such care and counseling in accordance with standardized guidance in the SSP Manual. While maintaining participant confidentiality, study sites may engage their CAB in exploring the social context surrounding instances of social impacts, to minimize the potential occurrence of such an impact.

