## 8.6.3 Exploratory Analysis

The data analysis plan is described below for each exploratory endpoint defined in Section 8.2.3.

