#### Discontinuation due to adverse events

The number and percentage of participants who discontinue study product administration and who terminate the study early will be tabulated by reason, grade and treatment arm. For any reasonably common AEs ( $> \sim 20$  events), exploratory analyses will be conducted to assess correlates of the AE, including demographics and duration and patterns of PrEP use, within the limits imposed by the small expected number of events.

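### The social-harm safety endpoint is defined for one ambiguously named arm, so as written it leaves unused the randomised comparison available up to Week 26

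*Combined protocol and SAP*

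**What the plan says.** Section 8.2.3 introduces the safety list with "Consistent with the exploratory study objective to assess safety of the intervention, the following endpoint(s) will be assessed". It names three items: reasons for stopping any study product, "Grade 3 and above adverse events", and "Social harms reported by participants in the intervention arm". Only the last is restricted to an arm, and no reason is given.

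Section 7.6 describes how these reports arise and are gathered. The stated source is general: "It is possible that participants' involvement in the study could become known to others, and that a social impact may result". Collection is general too: "Social impacts will be collected and reported on applicable eCRF(s) during regular visits". Neither sentence separates the arms.

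Section 8.6.3 opens with "The data analysis plan is described below for each exploratory endpoint defined in Section 8.2.3". Its paragraph on discontinuation says that the numbers who stop study product and who "terminate the study early will be tabulated by reason, grade and treatment arm". No paragraph there deals with social harms.

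Section 3.1 confines the difference in services between the arms to the first 6 months. After that, all participants receive co-located care and peer navigation.

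**The concern.** The objective is the safety of the intervention, and the trial has a randomised control for it during the first 26 weeks. An endpoint that counts social harms in one arm makes no use of that control. A reader of the result would see how many participants reported a harm, but not whether the number was higher or lower than among participants who were in the study without co-located care and peer navigation. It could plausibly go either way, because the intervention adds active peer outreach and also aims to reduce barriers linked to stigma.

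The label adds a second difficulty. With an Immediate Intervention Arm and a Deferred Intervention Arm, and with both on the intervention from Month 6, the singular phrase can be read in two ways. No period is attached to it.

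**Working it through.** **Is there a figure to reproduce?** No. The documents give no rate, sample size or power for social harms. The arm sizes come from Section 8.3 and Table 7: about 310 enrolled 1:1 gives 310 / 2 = 155 per arm, and 131 per arm is the number needed after 15% attrition. These agree with each other: 262 / 0.85 = 308.2, or 309 rounded up, against about 310 stated.

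**The texts side by side**

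- Collection (7.6): no limit by arm.
- Sister safety endpoints (8.2.3): no limit by arm.
- Discontinuations (8.6.3): tabulated by treatment arm.
- Social-harm endpoint (8.2.3): one arm.
- Social-harm analysis (8.6.3): none, although the section promises one for each exploratory endpoint.
- The other endpoint touching on social impact, the one on experience in the trial (8.2.3): "Qualitative and quantitative evaluations will be performed at the termination visit". By then both arms have been offered the intervention since Month 6, so it does not supply the missing contrast.

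**The two readings of the label**

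- If it means the randomised Immediate Arm, the group is fixed throughout and the Deferred comparator is left out. The footnote in Section 8.4 that contrasts intervention with Deferred intervention arms favours this reading.
- If it means anyone receiving the intervention, Deferred participants enter after Month 6 and the count mixes randomised groups and periods.

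Neither reading gives a comparison between randomised arms.

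**What the one-arm count leaves open.** Assume 10% of 155 in the Immediate Arm report a harm by Week 26, and vary the assumed Deferred rate p0. The 95% half-width is 1.96 × √[0.10 × 0.90/155 + p0(1 − p0)/155].

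| Deferred rate (assumed) | Difference | Half-width |
|---|---|---|
| 2% | +8 points | 5.2 |
| 5% | +5 points | 5.8 |
| 10% | 0 points | 6.7 |
| 15% | −5 points | 7.3 |

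The one-arm result is 10% in all four rows.

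**What a two-arm table would give.** With equal rates p and n per arm, the half-width is 1.96 × √[2p(1 − p)/n].

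- p = 5%, n = 155: 1.96 × √(0.095/155) = 4.9 points
- p = 10%, n = 155: 1.96 × √(0.18/155) = 6.7 points
- p = 5%, n = 131: 1.96 × √(0.095/131) = 5.3 points
- p = 10%, n = 131: 1.96 × √(0.18/131) = 7.3 points

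For a test at two-sided 0.05 with 80% power and 155 per arm, the detectable contrasts are 5% against 14.4% and 10% against 21.6%. With 131 per arm they are 5% against 15.4% and 10% against 22.8%.

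**The case against.** The strongest reply is that nothing is lost. Deferred-arm reports are collected, serious or unexpected social impacts go to the IRBs regardless of arm (7.6), the Study Monitoring Committee reviews all safety data (8.9), and Section 8.6 leaves technical detail to a separate analysis plan. A one-line exploratory item does not forbid tabulating the other arm. This stands as far as it goes. A reader might infer that the Deferred-arm data are thrown away, or that harms from the intervention can never be separated from background. The documents support neither, since reporting both arms mends the gap.

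A reader might also infer that after Month 6 the phrase no longer identifies any group. That fails if it means the randomised Immediate Arm, which stays a fixed group. The supportable criticism is ambiguity.

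A third tempting step is to argue that heavy background stigma swamps the count. Sections 7.6 and 9.3 frame these events as consequences of participation becoming known, so some attribution is built into what is collected. Misattribution remains possible, but the argument from background is weaker than it looks. It also does not remove the need for a comparator, because participation can become known in either arm.

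Finally, the proposed contrast has its own limits. The trial is open-label, and the extra peer contact in the Immediate Arm may change how often harms are reported. The rates above are assumptions, and 155 per arm presumes full retention. These points limit how the comparison can be interpreted, but they are not reasons to omit it.

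**Conclusion.** The point holds as a defect in an exploratory endpoint and its analysis. Data collection is sound. As written, Section 8.2.3 yields a count in one ambiguously labelled arm, out of line with the other safety endpoints, and Section 8.6.3 has no analysis for it. The unused comparison is modest in precision: about 4.9 to 6.7 points either side with 155 per arm, or 5.3 to 7.3 with 131, at assumed rates of 5% to 10% that have no source in the documents. At 5% the half-width is about as large as the rate itself, so the comparison would be descriptive and could not exclude a moderate excess. No primary or secondary result, sample size or decision rule depends on it. It is worth making because it improves how the stated safety objective is addressed at almost no cost.

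**What to change.** In Section 8.2.3, replace the item with: *Social harms (social impacts as in Section 7.6) reported by participants in each randomised arm*. This also settles the change of term between the two sections.

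In Section 8.6.3, add a short paragraph and one table. Give the number and percentage of participants reporting a social harm by randomised arm for Enrollment to Week 26, with the difference and its 95% confidence interval. Show later events separately by arm, without treating them as a comparison of intervention with control. Events may be few (155 × 0.05 is about 8 per arm), so name an interval method suited to small counts. State that the comparison is exploratory, and note open-label reporting and the extra peer contact in the Immediate Arm as limits.

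The cost is one reworded line, one paragraph and one table. No new data, visits or participants are needed.

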### 8.3 Sample Size

There is limited data on PrEP uptake and adherence specific to the TGW population, with the published data being highly variable. Moreover, the TGW population is a hard to reach population requiring multiple sampling and recruitment strategies. Given the unique challenges described above, the sample size is determined on the basis of the statistical power to detect a hypothesized difference in proportions between the Immediate vs Deferred Intervention arms, taking logistical and operational constraints regarding recruitment of HIV-uninfected TGW into consideration.

Figure 5 shows the number of individuals needed per study arm to achieve 90%, 85%, and 80% statistical power to detect a pre-determined difference in proportions  $p_1 - p_0$  between the Immediate Intervention Arm vs the Deferred Intervention Arm, under 1:1 randomization, with  $p_1$  and  $p_0$  denoting the proportion of HIV-uninfected TGW satisfying the condition of interest in the Deferred and Immediate Intervention Arms respectively. The horizontal axis depicts a range of plausible values of  $p_1 - p_0$ .

**Figure 5.** Sample sizes needed to achieve power (80%, 85%, 90%) for a two-sided test in proportions for an individually randomized trial with 1:1 randomization based on different values of hypothesized differences in proportions. For PrEP adherence, the hypothesized value under the alternative is 0.2.

Current research on PrEP uptake is limited, although existing data show low rates of PrEP uptake among TGW. Among HIV-uninfected TGW randomized to the Immediate Intervention vs. Deferred Intervention Arms, the study is being powered to detect a 20 percentage-point difference in PrEP adherence and a 25 percentage-point difference in PrEP uptake between the Deferred Intervention Arm and Immediate Intervention Arm at Week 26. We assume that the uptake, adherence and retention rates will be the same for the two PrEP agents (FTC/TAF and FTC/TDF).

We determine the conservative sample sizes needed to detect a difference of  $p_1 - p_2$  between proportion of HIV-uninfected TGW adhering to PrEP between the Deferred and Immediate Intervention Arms at week 26, targeting 90% power to detect statistically significant differences at the alpha 0.05-level based on a two-sided test in proportions. A total of 262 HIV-uninfected TGW will be needed to achieve 90% statistical power for detecting a difference in proportions of 20% adhering to PrEP between the Deferred vs Immediate Intervention Arms. This sample size also satisfies power requirements for PrEP uptake. Assuming an ~85% retention rate throughout the primary 6-month follow-up period, we will target enrolling total of approximately 310 HIV uninfected TGW individuals into study. Projected sample sizes are shown in Table 7. Equal 1:1 randomization is being used.

**Table 7. Projected Sample Size detecting the assumed differences in proportions at the end of 6-months with 90% power.**

	n 1	n 2	n needed	n required (accounting for 15% attrition)	Δ in Proportions (p)	Outcome
PrEP Adherence	131	131	262	310	0.20	Proportion adherent to PrEP at 6 months

^ Initial baseline prevalence estimates derived from studies of TGW women currently in the field.

#### 8.4 Accrual and Retention

Approximately 310 HIV-uninfected TGW will be enrolled and randomized to the Immediate and Deferred Intervention Arms across the five study sites. An average annual retention rate of at least 85 percent will be targeted. Differential enrollment targets will be considered for the sites, with higher enrollment targeted for the Brazil site and competitive enrollment among remaining U.S sites. We estimate 560 TGW will be screened for the study to achieve the enrollment target of approximately 310 TGW (80% of TGW screened).

a Considering that the variance, and therefore sample size is largest when  $p=0.5$ , we obtain conservative sample sizes by setting  $H_0: 0.5 - d/2$  and  $H_1: 0.5 + d/2$ , where  $d$  is the hypothesized difference in proportions between intervention and Deferred intervention arms.

b Note that since the hypothesized effect size for PrEP adherence is smaller than for PrEP uptake (20% vs 25%), the sample size needed to achieve 90% power based on PrEP adherence will also achieve greater power for PrEP uptake, hence powering the sample size for the prevention cohort study on PrEP adherence.

## **8.5 Random Assignment/Study Arm Assignment**

A stratified/block randomized trial will be used, stratifying differentially by site. Differential number of TGW will be enrolled at each site and randomized 1:1 using a random number generator to each study arm.

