## **8.6 Statistical Analysis**

This section briefly describes the final study analyses. Detailed technical specifications of the statistical analyses will be described in a separate Statistical Analysis Plan.

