### **8.6.1 Primary Analyses**

Study arms will be compared for baseline characteristics using descriptive statistics.

For each study visit, PrEP uptake will be defined as the proportion of TGW who initiate PrEP at any time up to and including that given visit among all TGW enrolled in the trial. PrEP uptake will be compared between study arms at the end of Week 26 for the primary objective. Confidence limits will be computed using the binomial distribution.

At each quarterly visit, the proportion of TGW adherent to PrEP is defined as the proportion of enrolled TGW who have confirmed protective levels of PrEP in their blood at that study visit. PrEP adherence (using either TDF or TAF-based regimens) will be **assessed objectively** using thresholds established by recently completed DOT studies. TGW who are missing drug level assessments, and who do not have drug dispensed at their most recent visit will be defined as non-adherent at that visit. The proportion of TGW determined to be adherent at Week 26 will be compared between the two study arms for the primary objective. Confidence limits will be computed using the binomial distribution.

PrEP persistence is defined as the average of each participant's mean number of visits adherent to daily PrEP. The mean number of visits adherent to daily PrEP will be (i) zero for TGW who never initiate PrEP during the study and (ii) the proportion of visits where the participant was confirmed to have protective levels of PrEP (using either TDF or TAF-based regimens) in blood according to objective thresholds established by recently completed DOT studies. PrEP persistence will be compared between study arms.

To assess acceptability in future use of the study intervention, the percentage (with 95% CI) of participants who report an interest in future use of co-located GAHT and peer-delivered health navigation model for HIV prevention in the future will be calculated among those enrolled in each study arm.

Descriptive summaries will be used to summarize and assess different aspects of feasibility such as recruitment, retention, and frequency and content of Peer Health Navigator contacts (text message, email, phone, in-person).

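### Randomisation is stratified by site, but the Week 26 uptake and adherence comparisons in section 8.6.1 do not mention site; stratifying them costs essentially nothing (minor)

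*Combined protocol and SAP*

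**What the plan says.** On randomisation, section 8.5 states: "A stratified/block randomized trial will be used, stratifying differentially by site". Allocation is 1:1 at each of five sites, four in the United States and one in Brazil. Site sizes will be unequal, "with higher enrollment targeted for the Brazil site and competitive enrollment among remaining U.S sites" (section 8.4).

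On the primary comparisons, section 8.6.1 states "PrEP uptake will be compared between study arms at the end of Week 26 for the primary objective" and "The proportion of TGW determined to be adherent at Week 26 will be compared between the two study arms for the primary objective". It gives binomial confidence limits for both and does not mention site. It defines both proportions among all enrolled participants.

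The only test named anywhere for these endpoints is in section 8.3, where the sample size is "based on a two-sided test in proportions".

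The adjustments foreseen are conditional. Section 8.6.1 provides for adjustment for PrEP agent if the arms are imbalanced, and for similar methods if missingness differs between arms. Section 8.6.4 says baseline predictors of missing outcomes may be considered as covariates. Neither section names site.

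Section 8.6 limits its own scope: "This section briefly describes the final study analyses", and "Detailed technical specifications of the statistical analyses will be described in a separate Statistical Analysis Plan". That separate plan is not part of the document reviewed.

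**The concern.** Blocked randomisation within site balances the arms at each site, so differences between sites add almost nothing to the true variance of the treatment difference. An unstratified analysis still counts those differences as noise. If site predicts uptake or adherence, its standard error is too large, its test rejects too seldom under the null, and its interval is too wide.

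The documents give no site-level rates, so whether site matters is unknown. There are reasons to expect that it may: two countries, only Truvada offered in Brazil (section 5.2), site-specific recruitment (section 4.4), and site-specific partner institutions for the deferred arm (section 3.1). The adjustment for PrEP agent does not replace site, because it is conditional, and U.S. participants choose the agent and may switch.

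What is at stake is precision, not validity. Section 1.2 says the trial is meant to inform the sample size of a full-efficacy trial, so the width of the interval for the difference matters as well as the p-value. Section 8.6.1 also leaves open whether its binomial limits apply to each arm or to the difference. If they are per arm, it specifies no interval for the difference.

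**Working it through.** **Inputs from the plan.** Two-sided alpha 0.05, 90% power and 1:1 allocation. Section 8.3 is explicit on the effects: "the study is being powered to detect a 20 percentage-point difference in PrEP adherence and a 25 percentage-point difference in PrEP uptake". A footnote in section 8.4 sets the planning rates symmetrically about 0.5, so 0.40 versus 0.60 for adherence. Retention at six months is about 85%, and there are five sites.

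**The plan's own figure.** With the variance fixed at p = 0.5:

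n per arm = 2 × 0.25 × (1.95996 + 1.28155)² / 0.20² = 131.3, consistent with 131 per arm and 262 in total.

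262 / 0.85 = 308, consistent with about 310. The sample size reproduces and is not in question.

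**Why the unstratified interval is too wide.** The pooled variance p(1 − p) is the average within-site variance plus the between-site variance (SD²). Under site-stratified allocation only the first part contributes to the variance of the difference, so approximately

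excess width = √[ p(1 − p) / (p(1 − p) − SD²) ] − 1.

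At 0.40 or 0.60, p(1 − p) = 0.24:

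- SD 0.07: √(0.24 / 0.2351) − 1 = 1.0%
- SD 0.13 to 0.15: √(0.24 / 0.2231) − 1 = 3.7% to √(0.24 / 0.2175) − 1 = 5.0%
- SD 0.19 to 0.21: √(0.24 / 0.2039) − 1 = 8.5% to √(0.24 / 0.1959) − 1 = 10.7%

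**Simulation.** 200,000 trials per scenario compared a pooled two-proportion z test with Wald interval against a Cochran-Mantel-Haenszel (CMH) test (no continuity correction) with a Mantel-Haenszel risk difference and Sato variance.

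All site sizes and rates are assumptions. Sizes per arm were 38/24/24/23/23 (132, which is 85% of 310 divided by 2) and 45/28/28/27/27 (155, all enrolled). Deferred-arm rates were 40% throughout; 30/35/40/45/50%; 20/30/40/50/60%; and 10/25/40/55/65%. Their between-site SDs are 0, 0.07, 0.13-0.15 and 0.19-0.21. Each unequal set was run with the largest site lowest, highest and in the middle; ranges cover these orders.

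Adherence, +20 points, 132 per arm (unstratified vs stratified):

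| Site rates | Power | Half-width | Excess width | Type I error, unstratified |
|---|---|---|---|---|
| 40% throughout | 91.3% vs 90.9% | 0.118 vs 0.118 | 0% | 5.2% |
| 30-50% | 91.6-91.7% vs 91.5-91.6% | 0.118 vs 0.116-0.117 | 0.9-1.2% | 4.8-5.0% |
| 20-60% | 92.2-92.4% vs 92.5-92.8% | 0.118 vs 0.112-0.113 | 4.0-4.9% | 3.9-4.3% |
| 10-65% | 93.1-93.5% vs 94.5-95.3% | 0.117-0.118 vs 0.106-0.109 | 8.3-10.6% | 2.9-3.4% |

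CMH type I error is 4.9-5.2% throughout. At +20 points, coverage of the Sato interval is 94.7-95.1%. At 132 per arm, coverage of the unstratified interval rises from 94.8% with no site differences to 96.6-96.9% at 10-65%.

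Adherence at 155 per arm: power 94.1% vs 94.1% with no site differences, 94.3-94.4% vs 94.6-94.8% at 30-50%, 94.8-95.0% vs 96.0-96.2% at 20-60%, and 95.5-96.0% vs 97.1-97.7% at 10-65%.

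Uptake, +25 points, 155 per arm: power 99.3% vs 99.4% with no site differences and 99.6-99.7% vs 99.8-99.9% at 10-65%. Half-width at 10-65% is 0.107 vs 0.097-0.099. The gain is in interval width only.

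**Sensitivity.** With a common odds ratio across sites and 131 per arm (100,000 trials per scenario), power was 91.2% both ways with no spread and 94.1% vs 96.7% at deferred-arm rates of 10-73%. Unstratified type I error there fell to 2.6%, against 5.0% for CMH. With very unequal sites (60/30/24/13/5 per arm), CMH type I error was 4.9-5.3% and Sato coverage 94.8-95.1%, so small sites need no pooling rule.

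**The case against.** The strongest reply is that section 8.6 calls itself brief and sends technical detail to a separate SAP. Whether a test is stratified is that kind of detail, and a sample-size formula does not commit the final analysis to ignoring site. This stands as a limit on the claim: the protocol is silent on the stratifier, which is different from saying site will be left out.

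Second, no conclusion is endangered. There is no bias, and adherence power exceeds 91% unstratified in every scenario, against a target of 90%. The 8-11% excess width and most of the 2-point gain need site rates spread over 10-65%, which the documents neither support nor exclude. All of this is correct and is why the point is minor.

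Third, the improvement may not be strictly free: at 132 per arm with no site differences, power falls from 91.3% to 90.9%. That loss is confined to 132. There is essentially none at 131 or 155 per arm, so it reflects the discreteness of the unstratified test at that size.

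Fourth, CMH is one choice among several. Site as a covariate in a regression would also respect the stratifier. The same reasoning extends to PrEP persistence, and the fit with the conditional adjustments in sections 8.6.1 and 8.6.4 would need a line in the SAP. These are reasonable extensions and do not weaken the recommendation.

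**Conclusion.** The concern holds, as a minor one. Site is the randomisation stratum and is absent from the Week 26 comparisons as written. If they are run unstratified, the cost depends on how much sites differ: nothing if they do not, about 1% excess interval width at modest differences, and 8-11% with up to 2 points of adherence power at wide ones. The direction is always conservative. The planned sample size and power are unaffected. These sizes rest on assumed site rates and site sizes. The silence itself rests on the protocol text alone, and the separate SAP may already resolve it.

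**What to change.** In section 8.6.1 and the SAP, add:

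> The Week 26 comparisons of PrEP uptake and PrEP adherence will be stratified by site, using a two-sided Cochran-Mantel-Haenszel test and a site-stratified (Mantel-Haenszel) risk difference with 95% CI (Sato variance). Binomial limits will be given for each arm's proportion. The unstratified comparison will be a sensitivity analysis.

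If the separate SAP already says this, only section 8.6.1 needs aligning. The cost is three sentences, which can wait for the next amendment, and the matching SAP text. No new data are needed.
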